2.1.4.2. Primary Safety Estimands – Infant Participants

- **Percentage of infant participants with specific birth outcomes.**

This estimand includes the following 4 attributes:

- Population: Infant participants born to maternal participants receiving 1 dose of investigational product.
- Variable: Presence/absence of specific birth outcomes (see [Appendix 1](#)).
- Intercurrent event(s): No intercurrent events to be considered.
- Population-level summary: Percentage of infant participants with specific birth outcomes in each group.

- **Percentage of infant participants having AEs from birth to 1 month of age.**

This estimand includes the following 4 attributes:

- Population: Infant participants born to the maternal participants receiving 1 dose of investigational product.
- Variable: Presence/absence of AEs from birth to 1 month.

- Intercurrent event(s): For participants who discontinue, all collected data will be included; missing AE dates will be imputed as described in Pfizer's Vaccine Statistics Rulebook.
- Population-level summary: Percentage of infant participants with AEs from birth to 1 month of age in each group.
- **Percentage of infant participants with SAEs and NDCMCs from birth through 6 and 12 months.**

This estimand includes the following 4 attributes:

- Population: Infant participants born to the maternal participants receiving 1 dose of investigational product.
- Variable: Presence/absence of SAEs and NDCMCs from birth through 6 and 12 months of life.
- Intercurrent event(s): For participants who discontinue, all collected data will be included; missing AE dates will be imputed as described in Pfizer's Vaccine Statistics Rulebook.
- Population-level summary: Percentage of infant participants with the event of interest during the first 6 and 12 months of life in each group.
- **Percentage of infant participants with SAEs and NDCMCs from birth through 24 months.**

This estimand includes the following 4 attributes:

- Population: Infant participants born to the maternal participants enrolled during the first year of the study and who received 1 dose of investigational product.
- Variable: Presence/absence of SAEs and NDCMCs from birth through 24 months of life.
- Intercurrent event(s): For participants who discontinue, all collected data will be included; missing AE dates will be imputed as described in Pfizer's Vaccine Statistics Rulebook.

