- Population-level summary: Percentage of infant participants with the event of interest during the first 24 months of life in each group and percentage of infant participants with the event of interest between 12 and 24 months of life in each group.

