4. ANALYSIS SETS (POPULATIONS FOR ANALYSIS)

Data for all participants will be assessed to determine if participants meet the criteria for inclusion in each analysis population prior to unblinding and releasing the database and classifications will be documented per standard operating procedures.

Population	Description
Enrolled	All participants who sign the informed consent document.
Randomly assigned to investigational product	All maternal participants who are assigned a randomization number in the IRT system.
Evaluable efficacy – infant (per-protocol)	All infant participants who are born to maternal participants who did not have major protocol deviations prior to the delivery and who received the investigational product to which they were randomized at least 14 days prior to delivery, are eligible, and have no major protocol deviations.
ITT efficacy – infant	All infant participants who are born to vaccinated maternal participants.
Evaluable immunogenicity – infant	All infant participants who are born to maternal participants who did not have major protocol deviations prior to the delivery and who received the investigational product to which they were randomized, are eligible, have blood drawn for assay testing within the specified time frame, ^a have valid and determinate assay results for the proposed analysis, and have no major protocol deviations.
Evaluable immunogenicity – maternal	All maternal participants who are eligible, receive the investigational product to which they were randomized, have blood drawn for assay testing within the specified time frame, ^b have valid and determinate assay results for the proposed analysis, and have no major protocol deviations.
ITT immunogenicity – infant	All infant participants who are born to vaccinated maternal participants and have at least 1 valid and determinate assay result for the proposed analysis.
ITT immunogenicity – maternal	All randomized maternal participants who receive investigational product and have at least 1 valid and determinate assay result for the proposed analysis.
Safety – infant	All infant participants who are born to vaccinated maternal participants.
Safety – maternal	All randomized maternal participants who receive investigational product.

- a. A cord blood sample must be obtained on the day of birth. If cord blood is unavailable, a venous blood sample may be collected from the infant preferably within 24 hours but up to 7 days after birth.

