6.1.1.1.1. Main Analysis

- Estimand strategy: Hypothetical.
- Analysis set: Evaluable efficacy – infant ([Section 4](#)).
- Analysis methodology: VE will be analyzed using a conditional exact test based on the binomial distribution of the number of disease cases in the RSV vaccine group, given the total number of cases in both groups.
- Intercurrent events and missing data: All postdiscontinuation or postviolation observations will be censored; such events include the infant receiving palivizumab or another monoclonal antibody targeting RSV and the infant receiving transfusions of more than 20 mL/kg of any blood products at ≤ 180 days of age.
- For each group, the number (n), percentage, and 95% CI of RSV-positive MA-LRTI cases occurring within 90 days, 120 days, 150 days, and 180 days after birth, as confirmed by the EAC, will be presented for each group. Severe MA-LRTI cases are a subset of MA-LRTI cases, and all severe MA-LRTI cases will also be considered MA-LRTI cases.

- VE compared to placebo along with the corresponding 100(1- alpha)% CI (adjusted for the interim) will be presented. This will be based on raw numbers of cases and also with an adjustment for any differences in follow-up time. See [Section 5.1](#) for testing procedures.
- Kaplan-Meier curves showing accrual of cases for this endpoint over 180 days will be presented.

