6.1.2.3. SAEs and NDCMCs From Birth Through 6 and 12 Months of Age

- Analysis set: Safety – infant ([Section 4](#)).
- Analysis methodology: Descriptive summary statistics.
- Intercurrent events and missing data: For participants who discontinue, all collected data will be included; missing AE dates will be imputed as described in Pfizer’s Vaccine Statistics Rulebook.
- For each group, the number of participants with SAEs and NDCMCs through 6 and 12 months of age (n), percentage, and 95% CI will be presented (in separate outputs) for any event, each SOC, and each PT within each SOC, by vaccine group.

6.1.2.4. SAEs and NDCMCs From Birth Through 24 Months of Age (for Infants Born to Maternal Participants Enrolled During First Year of the Study)

- Analysis set: Safety – infant ([Section 4](#)).
- Analysis methodology: Descriptive summary statistics.
- Intercurrent events and missing data: For participants who discontinue, all collected data will be included; missing AE dates will be imputed as described in Pfizer’s Vaccine Statistics Rulebook.

- For each group, the number of participants with SAEs and NDCMCs (in separate outputs) through 24 months of age (n), percentage, and 95% CI will be presented for any event, each SOC, and each PT within each SOC, by vaccine group.
- For each group, the number of participants with SAEs and NDCMCs (in separate outputs) between 12 and 24 months of age (n), percentage, and 95% CI will be presented for any event, each SOC, and each PT within each SOC, by vaccine group.

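### The 12–24 month infant SAE/NDCMC percentage inherits a population fixed at birth, so infants who withdrew before 12 months dilute it; show an at-risk denominator and an infant-year rate beside it

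*SAP*

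**What the plan says.** Section 2.1.4.2 defines the population of the 24-month SAE/NDCMC estimand as "Infant participants born to the maternal participants enrolled during the first year of the study and who received 1 dose of investigational product". The intercurrent-event rule is "For participants who discontinue, all collected data will be included; missing AE dates will be imputed as described in Pfizer's Vaccine Statistics Rulebook". The population-level summary has two parts: the percentage with an event in the first 24 months, and the "percentage of infant participants with the event of interest between 12 and 24 months of life in each group". The second part has no population, variable or intercurrent-event rule of its own.

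Section 6.1.2.4 names Safety – infant as the analysis set. Section 4 defines that set as "All infant participants who are born to vaccinated maternal participants", and the heading of 6.1.2.4 limits it to first-year infants. The planned output for the late window is the number of infants with an event "between 12 and 24 months of age (n), percentage, and 95% CI will be presented for any event", each SOC and each PT, by group. No between-group difference, person-time rate or time-to-event summary is planned for this endpoint.

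For the primary efficacy endpoints, Section 6.1.1.1.1 says of VE: "This will be based on raw numbers of cases and also with an adjustment for any differences in follow-up time".

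**The concern.** A denominator counted from birth is natural for a window that opens at birth. This window opens 12 months later. An infant who withdrew at, say, month 3 can supply no observed event between 12 and 24 months, yet belongs to the stated population and is in effect counted as event-free. The rule on discontinuation settles which data are kept. It does not settle who is at risk when a later window opens.

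Section 2.2 gives longer-term safety oversight as one purpose of the 24-month follow-up. If the late-window percentage is diluted by infants who were no longer observed, that percentage and its confidence interval sit too low as estimates of risk in the second year of life. If more infants leave one arm than the other, the dilution differs by arm and appears as a small safety difference, or masks one.

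**Working it through.** **No figure to reproduce.** The SAP states no SAE/NDCMC rate, attrition rate or expected count for this window. All values of p and d below are assumptions.

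**Which denominator follows from the text.** The estimand population (2.1.4.2) is fixed at birth and restricted to first-year infants. The analysis set (Section 4, applied in 6.1.2.4) is also fixed at birth. Neither section requires an infant to be in follow-up at 12 months. The natural reading is therefore N = all first-year infants born to dosed mothers.

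**Size within one arm.** Let p be the 12–24 month risk among infants still followed at 12 months, and d the share withdrawn before 12 months. The reported percentage is p × (1 − d), so the relative understatement is d. At p = 5%:

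| d | Reported on the birth denominator | On infants in follow-up at 12 months | Shortfall (points) |
|---|---|---|---|
| 2% | 4.90% | 5.00% | 0.10 |
| 5% | 4.75% | 5.00% | 0.25 |
| 10% | 4.50% | 5.00% | 0.50 |
| 15% | 4.25% | 5.00% | 0.75 |
| 20% | 4.00% | 5.00% | 1.00 |

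Over d = 2% to 20%, the shortfall is 0.04 to 0.4 points at p = 2% and 0.2 to 2.0 points at p = 10%.

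**Loss inside the window.** If a further 5% of those remaining leave evenly between 12 and 24 months, the observed share of the window is (1 − d) × (1 − 0.05/2). For d = 5% this is 0.95 × 0.975 = 0.926, and for d = 20% it is 0.80 × 0.975 = 0.78. The understatement becomes about 7% and 22%. A 12-month at-risk denominator does not recover this extra part; a rate per infant-year does, if censoring is uninformative.

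**Effect on the comparison of arms.** With the same true risk in both arms, the apparent ratio is (1 − d₁)/(1 − d₂):

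- 5% vs 5%: 0.95/0.95 = 1.00
- 5% vs 7%: 0.95/0.93 = 1.02 (4.75% vs 4.65% at p = 5%)
- 5% vs 10%: 0.95/0.90 = 1.06 (4.75% vs 4.50%)
- 5% vs 15%: 0.95/0.85 = 1.12 (4.75% vs 4.25%)
- 10% vs 20%: 0.90/0.80 = 1.13 (4.50% vs 4.00%)

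**Scale against sampling error.** Take 5,000 infants per arm, which is the whole 10,000 enrolment ceiling of Section 2.2 at one infant per mother and so at least as large as the first-year subset. The standard error of a difference near 5% is √(2 × 0.05 × 0.95 / 5,000) = 0.44 points. The 0.25-point artefact from 5% vs 10% attrition is below one standard error. The 0.50-point artefact from a ten-point gap in attrition is just above one. A smaller subset has a larger standard error.

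**The case against.** The strongest reply is that nothing has been shown to be wrong. No sentence states N for the 12–24 month row, Section 2 places table shells and programming rules outside the SAP, and Section 5.2 has N shown with each percentage. This stands in part: the birth-based N is an inference, though the one that the stated population and analysis set lead to. If the shells use another N, the SAP still needs to say so.

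Other parts of the reply stand in full:

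- **Deaths.** A reader might infer that infants who died before 12 months bias the figure in the same way. Under a population fixed at birth, having no event after 12 months is the true value for such an infant. Only withdrawal leaves an outcome unobserved.
- **Cumulative percentages.** A reader might infer that the 12- and 24-month percentages from birth score every early leaver as event-free. They do not: "For participants who discontinue, all collected data will be included", so a leaver with an earlier event counts. These are ordinary crude incidence proportions.
- **Contrast with efficacy.** VE is a confirmatory comparison. Section 6.6.1 treats safety analysis as generally exploratory, and 6.1.2.4 plans no between-arm test. Adjusting one for follow-up and not the other is no contradiction.
- **The remedy is not neutral.** A denominator of infants retained at 12 months conditions on a status that arises after randomisation, and a rate assumes uninformative censoring. This argues for adding these figures rather than substituting them.

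Section 6.5.2 tabulates withdrawals by group, so unequal attrition should be visible. That table does not correct the late-window percentage or its interval.

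**Conclusion.** The point holds in a limited form. The 12–24 month summary carries a population fixed at birth into a window that opens at 12 months. As written, it understates late-window risk by about the share of infants who withdrew early: 5–20% relative for an assumed 5–20% loss, somewhat more with further loss inside the window. The calculation takes as its target the risk among infants still followed at 12 months.

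A reader might go further and conclude that the arms are not comparable. The document does not support that. With equal retention the ratio is undistorted, nothing in the SAP suggests that retention will differ by arm, and plausible gaps give ratios of about 1.02 to 1.13 in a descriptive table. Nor do the cumulative percentages need to be replaced. This is a cheap improvement that makes one primary safety summary easier to interpret. It does not touch the efficacy analysis or the type I error.

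**What to change.** In Section 6.1.2.4, keep the 12–24 month percentage as planned and state its denominator. Add beside it, by arm:

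- (a) the number of first-year infants alive and in follow-up at 12 months, and the 12–24 month percentage on that denominator;
- (b) infants with at least one event in the 12–24 month window per 100 infant-years of follow-up in that window, with 95% CI.

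Add a sentence to the summary attribute in Section 2.1.4.2 that points to these figures. Footnote that (a) conditions on retention after randomisation and that (b) assumes uninformative censoring.

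The cost is a few lines of SAP text and one or two extra columns, from follow-up and event dates that the study should already record. Nothing planned is removed.

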2.1.4.3. Primary Safety Estimands – Maternal Participants

- Percentage of maternal participants reporting prespecified local reactions.**

This estimand includes the following 4 attributes:

- Population: Maternal participants who receive 1 dose of investigational product.
- Variable: Presence/absence of prespecified local reactions within 7 days after vaccination.
- Intercurrent event(s): For participants who discontinue, all collected data will be included; missing data will not be imputed.
- Population-level summary: Percentage of maternal participants reporting local reactions in each group.

- Percentage of maternal participants reporting prespecified systemic events.**

This estimand includes the following 4 attributes:

- Population: Maternal participants who receive 1 dose of investigational product.
- Variable: Presence/absence of prespecified systemic events within 7 days after vaccination.
- Intercurrent event(s): For participants who discontinue, all collected data will be included; missing data will not be imputed.
- Population-level summary: Percentage of maternal participants reporting systemic events in each group.

- Percentage of maternal participants reporting AEs from the time of vaccination through 1 month after vaccination.**

This estimand includes the following 4 attributes:

- Population: Maternal participants who receive 1 dose of investigational product.
- Variable: Presence of AEs within 1 month after vaccination.
- Intercurrent event(s): For participants who discontinue, all collected data will be included; missing AE dates will be imputed as described in Pfizer's Vaccine Statistics Rulebook.
- Population-level summary: Percentage of maternal participants reporting AEs through 1 month after vaccination in each group.

- **The percentage of maternal participants reporting SAEs throughout the study.**

This estimand includes the following 4 attributes:

- Population: Maternal participants who receive 1 dose of investigational product.
- Variable: Presence/absence of SAEs throughout the study.
- Intercurrent event(s): For participants who discontinue, all collected data will be included; missing AE dates will be imputed as described in Pfizer's Vaccine Statistics Rulebook.
- Population-level summary: Percentage of maternal participants reporting SAEs throughout the study in each group.

2.1.5. Secondary Estimands

2.1.5.1. Secondary Efficacy Estimands – Infant Participants

- **VE, defined as the RR reduction of hospitalization due to RSV occurring within 90 days, 120 days, 150 days, 180 days, and 360 days after birth in the RSV vaccine group compared to the placebo group.**

This estimand includes the following 4 attributes:

- Population: Infant participants born to maternal participants receiving 1 dose of investigational product and in compliance with the key protocol criteria (evaluable efficacy infant participants).
- Variable: Occurrence of hospitalization due to RSV occurring within 90 days, 120 days, 150 days, 180 days, and 360 days after birth as confirmed by the EAC.
- Intercurrent event(s): For participants who discontinue from the study or have major protocol deviations, all postdiscontinuation or postviolation observations will be censored; such events include the infant receiving palivizumab or another monoclonal antibody targeting RSV and the infant receiving transfusions of more than 20 mL/kg of any blood products at ≤ 180 days of age.
- Population-level summary: RR reduction of hospitalization due to RSV occurring up to 90 days, 120 days, 150 days, 180 days, and 360 days in the RSV vaccine group compared to the placebo group.

- **VE, defined as RR reduction of MA-LRTI due to any cause occurring within 90 days, 120 days, 150 days, 180 days, and 360 days after birth in the RSV vaccine group compared to the placebo group.**

This estimand includes the following 4 attributes:

- Population: Infant participants born to maternal participants receiving 1 dose of investigational product and in compliance with the key protocol criteria (evaluable efficacy infant participants).
- Variable: Occurrence of MA-LRTI due to any cause occurring within 90 days, 120 days, 150 days, 180 days, and 360 days after birth.
- Intercurrent event(s): For participants who discontinue from the study or have major protocol deviations, all postdiscontinuation or postviolation observations will be censored; such events include the infant receiving palivizumab or another monoclonal antibody targeting RSV and the infant receiving transfusions of more than 20 mL/kg of any blood products at ≤ 180 days of age.
- Population-level summary: RR reduction of MA-LRTI due to any cause occurring up to 90 days, 120 days, 150 days, 180 days, and 360 days in the RSV vaccine group compared to the placebo group.

- **VE, defined as the RR reduction of MA-LRTI due to RSV occurring within 210 days, 240 days, 270 days, and 360 days after birth in the RSV vaccine group compared to the placebo group.**

This estimand includes the following 4 attributes:

- Population: Infant participants born to maternal participants receiving 1 dose of investigational product and in compliance with the key protocol criteria (evaluable efficacy infant participants).
- Variable: Occurrence of MA-LRTI due to RSV occurring within 210 days, 240 days, 270 days, and 360 days after birth.
- Intercurrent event(s): For participants who discontinue from the study or have major protocol deviations, all postdiscontinuation or postviolation observations will be censored; such events include the infant receiving palivizumab or another monoclonal antibody targeting RSV and the infant receiving transfusions of more than 20 mL/kg of any blood products at ≤ 180 days of age.
- Population-level summary: RR reduction of MA-LRTI due to RSV occurring up to 210 days, 240 days, 270 days, and 360 days in the RSV vaccine group compared to the placebo group.

2.2. Study Design

This is a Phase 3, multicenter, randomized, double-blinded, placebo-controlled study to assess the efficacy, safety, and immunogenicity of bivalent RSVpreF or placebo (1:1 randomization) in infants born to healthy women vaccinated during pregnancy, and the safety and immunogenicity in the pregnant women. This will be a global study, including sites in both the northern and southern hemispheres, and it will span multiple RSV seasons.

This is an event-driven study with a target of 124 adjudicated (primary-endpoint) cases of MA-LRTI due to RSV (meeting the case definition in the per-protocol infant population described in [Section 9.2 of the protocol](#)). Vaccination of maternal participants will occur at a time of year such that the infant is likely to be exposed to seasonal RSV during the first 6 months of life. It was anticipated that approximately 6900 mother-infant pairs would be needed to accumulate 124 per-protocol cases prior to the global COVID-19 pandemic. With the variable RSV season, the sample size may need to be increased and enrollment could go up to 10,000 maternal participants based on the number of RSV cases.

Study-eligible pregnant women will be randomized in a 1:1 ratio to receive a single dose RSVpreF or placebo. The dose of RSV prefusion F antigen in RSVpreF for this study will be 120 µg (60 µg A and 60 µg B).

Assessments for mothers will include parameters to allow descriptions of safety, tolerability, and immunogenicity of the vaccine in maternal participants.

For all infant participants, data will be collected for any medically attended respiratory illness to assess for cases of LRTI due to RSV (efficacy endpoint). Additionally, throughout the study all respiratory illnesses, SAEs, and NDCMCs reported will be assessed in this population. Infant participants enrolled during the first year of the study will be followed up for 24 months after birth, to include longer-term RTI surveillance and safety oversight to address safety and the possibility of conferred enhanced protection (antibody persistence) during a second RSV season. All other infants will be followed up for 12 months after birth. All MA-RTIs meeting the protocol definition for a potential study endpoint will be adjudicated by an independent EAC. In addition, this study will use an E-DMC to monitor vaccine safety and efficacy and study futility.

